1. INTRODUCTION

1.1. Background

Pseudoxanthoma elasticum (PXE) is a rare, ectopic calcification disease due to autosomal recessive mutation in the ATP-binding cassette subfamily C member 6 (ABCC6) gene. The prevalence of PXE is estimated as approximately 1 in 50,000.^{1,2} Clinical manifestations of PXE are usually late onset, slowly progressive, and frequently not recognized until patients are in their 20s to 30s. PXE clinical signs are commonly seen in the skin, the eyes, and the cardiovascular system. Currently, there is no specific treatment for systemic manifestation of PXE except for antivascular endothelial growth factor (VEGF) ocular injection for choroidal neovascularization.

[figure not shown]
The molecular basis of PXE is the inactivating mutations in the gene encoding ABCC6, an ATP-dependent efflux transporter that is present mainly in the liver.³ Extracellularly, the excreted nucleoside triphosphate is hydrolyzed by ectonucleotidases to nucleoside monophosphate and inorganic pyrophosphate (PPi), the latter a potent endogenous inhibitor of mineralization. In PXE, the absence of ABCC6-mediated adenosine triphosphate release from the liver results in reduced PPi levels, leading to ectopic calcification.⁴

Pyrophosphate is rapidly degraded to inorganic phosphate by tissue-nonspecific alkaline phosphatase (TNAP), encoded by the ALPL gene. It has been hypothesized that inhibition of TNAP activities would increase endogenous substrate PPi levels, leading to amelioration of the ectopic mineralization phenotype in PXE.^{5,6} Indeed, a growing number of in vitro and in vivo pharmacology studies (including animal models of PXE) have confirmed and supported this approach.^{7,8,9}

1.2. Study Rationale

DS-1211b is a potent small-molecule inhibitor of TNAP being developed by Daiichi Sankyo for the treatment of ectopic calcification diseases such as PXE. In vitro and in vivo animal studies have shown that it is effective in inhibiting TNAP activities, increasing PPi levels, and reducing ectopic calcification.¹² CCI

Therefore, Danchi Sankyo is proceeding with this study in individuals with an established diagnosis of PXE to continue the development of DS-1211b for the treatment of PXE and potentially other progressive ectopic calcification diseases.

2. OBJECTIVES, OUTCOME MEASURES, AND ENDPOINTS

[figure not shown]
2.1. Study Objectives

The objectives, definitions of associated endpoints as well as applicable outcome measures are described in Table 2.1. Further requirements for the endpoint analyses and censoring rules, where applicable, can be found in Section 11.4 Section 11.5, and Section 11.6.

Study results, based on the analysis of below endpoints, will be analyzed to assess the dose for future clinical trials.

Table 2.1: Description of Objectives, Outcome Measures, and Endpoints

Objectives	Outcome Measure	Endpoints	Category				
Primary							
To assess the safety and tolerability of DS-1211b compared with placebo in subjects with PXE	Title: Safety parameters during the study Description: Descriptive statistics of safety endpoints Time frame: From the time the subject signs the study ICF and up to Day 98 (14 days after the last dose of study drugs)	Incidence of AEs, including SAEs, and treatment-emergent AEs, physical examination/assessment findings including vital sign measurements, standard clinical laboratory parameters, and ECGs	Safety				
To assess the dose response by assessing the treatment changes in PD endpoints	Title: PD endpoints Description: Profiles of ALP and TNAP substrates Time frame: Data are collected at baseline through Day 98.	ALP, PPi, and PLP	Pharmacodynamic				
Secondary							
To characterize the PK of DS-1211a (the free form of DS-1211b in plasma) in subjects with PXE Title: PK endpoints Description: Plasma concentration and PK parameters of DS-1211a Time frame: Data are collected at baseline through Day 84.		Plasma concentration and PK parameters of DS-1211a Include, but are not limited to, Cmax, Tmax, Ctrough, AUCtau, AUClast, and AUCinf (if possible to calculate)	Pharmacokinetic				

[figure not shown]
3. STUDY DESIGN

3.1. Overall Design

Study DS1211-A-U201 is a 12-week, randomized, double-blind, placebo-controlled, parallel-group study that aims to assess the safety, tolerability, and pharmacokinetic (PK) and pharmacodynamic (PD) dose response of DS-1211b in individuals with Pseudoxanthoma Elasticum (PXE) by using biomarkers relating to tissue-nonspecific alkaline phosphatase (TNAP) inhibition.

Eligible individuals with established diagnosis of PXE will be randomized to 1 of 4 arms in a 1:1:1:1 ratio, to receive DS-1211b or placebo in tablet form for once daily dosing (Figure 3.1), for a total of 12-week dosing,

Figure 3.1: Study Schema

F/U = follow-up

The study will be conducted at approximately 10 study sites located in the US and possibly in the European region.

The study start date is the date when the first study subject has signed the informed consent. A PXE individual will be considered as eligible for randomization when the Investigator or designee has obtained written consent and has confirmed all eligibility criteria have been met during the screening period and when all screening procedures have been completed.

Study safety assessments include physical examinations/assessments, adverse events (AEs), electrocardiogram, and safety laboratory tests.

[figure not shown]
The Schedule of Events (SoE) is presented in Table 3.1. An intraday schedule for Visit 2 to Visit 5 is presented in Table 3.2.

3.2. Discussion of Study Design

This safety, tolerability, and dose-ranging study will evaluate DS-1211b doses that will inhibit TNAP sufficiently

Safety, tolerability, PK, and mechanism of action (MOA)-related PD biomarkers (ALP, PPi, and PLP) will be assessed from the doses, doses, of DS-1211b versus placebo. TNAP inhibition increases PPi levels, the MOA by which DS-1211b is proposed to reduce ectopic calcification. However, excessive TNAP inhibition increases the risk of recapitulating clinical manifestations of hypophosphatasia (HPP), a genetic mineralization disorder of TNAP deficiency accompanied by abnormally and persistently elevated PPi and PLP levels. Therefore, a careful benefit-to-risk characterization of the extent of TNAP inhibition that achieves a balance between increases in PPi versus increases in PLP is critical for selecting a target DS-1211b dose for later studies.

The 3 doses proposed for this study cover the likely range of a clinically safe and effective dose, based on results from nonclinical pharmacology studies, completed studies in healthy volunteers (safety, TNAP inhibition, PPi and PLP), published literature in HPP (PLP and PPi), and literature in PXE (PPi), as discussed in Section 1.

These results will be used for modeling and simulation at the end of the study to further evaluate the eventual recommended clinical dose for future clinical trials.

3.3. Schedule of Events

Table 3.1: Schedule of Events

Period	Screening	Baseline	Tre	eatment	Period	Postdose	Follow-up	Notes
Visit Number	1	2	3	4	5 (EOT)	6	7	
Study Day	- 30 to -1	1	15	43	84ª	Last dose+3 ^{b,c}	98°	^a Or day of early discontinuation. ^b To be scheduled at 2 to 4 days after last dose (eg, Visit 5 or early discontinuation). ^c In-home visit unless otherwise specified by Investigator.
Window (days)			±3	±3	±3	±1	±5	
Eligibility Assessments								
Informed consent	X							Obtain prior to performing any study procedures
Inclusion/Exclusion	X							
Randomization		X						
Demographics	X							
History								
Medical/Surgical	X							
Safety Assessments								
Vital signs	х	Х	Х	X	Х	Х	X	Measurements include pulse, respiratory rate, body temperature, and systolic and diastolic blood pressure. Blood pressure to be recorded while subject is in recumbent position, having rested in this position for at least 5 minutes. Vital signs to be collected after ECGs and prior to blood draws
Height/Weight	X							
Physical examination	X	Х	X	X	X		X ^d	^d Physical assessment to be performed by visiting nurse for the in-home visit.

Period	Screening	Baseline	Tre	atment	Period	Postdose	Follow-up	Notes
Visit Number	1	2	3	4	5 (EOT)	6	7	
Study Day	- 30 to -1	1	15	43	84ª	Last dose+3 ^{b,c}	98°	^a Or day of early discontinuation. ^b To be scheduled at 2 to 4 days after last dose (eg, Visit 5 or early discontinuation). ^c In-home visit unless otherwise specified by Investigator.
Window (days)			±3	±3	±3	±1	±5	
Triplicate 12-lead ECG	X	х	х	X	X		X	 See Table 3.2 for detailed information on Visits 2 to 5. ECGs to be collected prior to vital signs and blood draws Triplicates at each collection Screening and follow-up visits (V1 and V7): 1 triplicate collection
AEs	X				X		All AEs occurring after the subject signs the ICF and up to Day 98 (14 days after last dose) should be collected.	
SAEs	Х				X		All SAEs occurring after the subject signs the ICF and up to Day 98 (14 days after last dose) should be collected.	
Medications and Nondrug Therapies								
Prior medications	Х							Medications used within 30 days prior to screening will be recorded. COVID-19 vaccination to be recorded regardless of time frame relative to screening.
Concomitant medications	X	X	X	X	X		X	
Laboratory Assessments								
Hematology	Х	Х	X	Х	Х		X	Fasting required. Blood collection should follow ECG and vital signs if indicated at same time point. See Section 9.8 for details
Coagulation	Х	X	X	Х	х		X	PT, aPTT and INR; predose (V2 to V5). Blood collection should follow ECG and vital signs if indicated at the same timepoint.
Chemistry	Х	X	X	Х	Х	Xe	X	Fasting required at all visits ^e except the postdose visit (Visit 6). Blood collection should follow ECG and vital signs if indicated at same timepoint. See Section 9.8 for details
Urine analysis	X	X			X			Fasted, use spot urine

Period	Screening	Baseline	Tre	atment	Period	Postdose	Follow-up	Notes
Visit Number	1	2	3	4	5 (EOT)	6	7	
Study Day	- 30 to -1	1	15	43	84ª	Last dose+3 ^{b,c}	98°	^a Or day of early discontinuation. ^b To be scheduled at 2 to 4 days after last dose (eg, Visit 5 or early discontinuation). ^c In-home visit unless otherwise specified by Investigator.
Window (days)			±3	±3	±3	±1	±5	
Pregnancy test	х	X	х	Х	Х		Х	Serum pregnancy tests to be performed at V1 Screening Visit. Urine pregnancy test to be performed at V2, V3, V4, V5, and V7. If positive, a serum pregnancy test should be performed.
Pharmacokinetic Assessments								
PK Sampling		X ^f	Xg	Xg	X^{f}			fFull collection/ § Sparse collection (See Table 3.2) Central laboratory testing. Blood collection should follow ECG and vital signs if indicated at same timepoint. Sampling will be obtained under nonfasted condition except for the predose samples, which will be collected after an overnight fast (≥ 8 hours). The windows for blood sample collection are as follows: 120 minutes at the predose timepoint and by ±10% of the nominal sampling time thereafter.
Pharmacodynamic Assessments								
ALP, PPi, and PLP	Xh	X ^f	Xg	Xg	X ^f	$\mathbf{X}^{\mathtt{h,i}}$	$X^{\mathrm{h,i}}$	fFull collection/g Sparse collection (See Table 3.2) h Single timepoint sample collection i ALP and PLP only Central laboratory testing. Blood collection should follow ECG and vital signs if indicated at same timepoint. All samples will be obtained under nonfasted condition except for the predose samples (Visits 2 to 5), which will be collected after an overnight fast (≥8 hours). The windows for blood sample collection are as follows: 120 minutes at the predose timepoint and by ±10% of the nominal sampling time thereafter.

Period	Screening	Baseline	Treatment Period			Postdose	Follow-up	Notes
Visit Number	1	2	3	4	5 (EOT)	6	7	
Study Day	- 30 to -1	1	15	43	84ª	Last dose+3 ^{b,c}	98°	 ^a Or day of early discontinuation. ^b To be scheduled at 2 to 4 days after last dose (eg, Visit 5 or early discontinuation). ^c In-home visit unless otherwise specified by Investigator.
Window (days)			±3	±3	±3	±1	±5	
								Study participants should withhold the intake of vitamin B6 or vitamin B6-containing supplements on the day of the study visits (Visit 1 to Visit 7) until the completion of the study procedures. See Section 6.3 for additional details.
CCI								procedures. See Section Sie 101 additional details.

Period	Screening	Baseline	Tre	Treatment Period		Postdose	Follow-up	Notes
Visit Number	1	2	3	4	5 (EOT)	6	7	
Study Day	- 30 to -1	1	15	43	84ª	Last dose+3 ^{b,c}	98°	 ^a Or day of early discontinuation. ^b To be scheduled at 2 to 4 days after last dose (eg, Visit 5 or early discontinuation). ^c In-home visit unless otherwise specified by Investigator.
Window (days)			±3	±3	±3	±1	±5	
CCI								
Study Drug (DS-1211b/placebo)								
Dispense		X		X				
Assess treatment compliance			X	X	X			
CCI								

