5.1.4. Emergency Unblinding Procedure

In the case of an emergency where, in the opinion of the Investigator, discontinuation of study drug is not sufficient and the study treatment must be unblinded in order to evaluate further a course of medical treatment, the Investigator can perform the unblinding, after discussion with the Medical Monitor, if possible. Entry of the Adverse Event case report form (CRF) page should be completed before unblinding except in cases where immediate treatment of the subject is required. If immediate treatment is required, the Adverse Event CRF page is to be completed within 24 hours of the unblinding.

In the event of an emergency unblinding, the subject will be informed about his/her treatment assigned. Information about the treatment assignment **must be** restricted to designated study site staff/personnel who are providing immediate care to the subject. Any documentation of the treatment assignment **must be** maintained separately (ie, a secured file). The information **must not be** included in the subject's source files to ensure the treatment assignment will remain blinded to the Contract Research Organization (CRO) monitor and other study personnel not involved with the subject's immediate care.

When an emergency unblinding has occurred, an automatic notification (via e-mail) will be sent to the Investigator and selected Daiichi Sankyo study personnel from the interactive response technology (IRT) vendor. The notification will not contain any unblinding information. This will trigger the follow-up process to document the unblinding by completing the Emergency

Unblinding by Investigator Form (to be provided by study personnel upon receipt of IRT notification) and submission to Daiichi Sankyo Clinical Safety and Pharmacovigilance; please refer to the form for completion instructions.

Once the study treatment has been unblinded for a specific subject, the study treatment should be discontinued for the subject, and the subject should leave the study treatment phase. The end of treatment and follow-up assessments for the subjects will be performed as defined in Section 6.4.

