5.7.2. Withdrawal Procedures

If a subject is withdrawn from the study, the Investigator will complete and report the observations as thoroughly as possible up to the date of withdrawal including the date of last treatment and the reason for withdrawal.

If the subject is withdrawn because of an adverse event, the Investigator will follow the subject until the adverse event has resolved or stabilized.

All subjects who are withdrawn from the study should complete protocol-specified early discontinuation/end of treatment procedures (Visit 5, and Visits 6 and 7: See Table 3.1).

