6.4. End of Treatment

Visit 5 (Day 84) is the end of treatment visit. Any study participant who discontinues early will complete early discontinuation assessment using the procedures outlined in the end of treatment visit and the follow-up assessments (Visits 6 and 7).

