9.2. Adverse Event Collection and Reporting

All AEs (see Section 9.4.1 and Section 9.4.2 for definitions) occurring after the subject signs the Informed Consent Form and up to $14 (\pm 5)$ days after the last dose of study medication (ie, the follow-up period), whether observed by the Investigator or reported by the subject, will be recorded on the Adverse Event CRF page. All SAEs will be followed until resolution, stabilization, the event is otherwise explained, or the participant is lost to follow-up.

Medical conditions (including clinically significant laboratory values/vital signs that are out of range) that were diagnosed or known to exist prior to the consent date will be recorded as medical history, and not an Adverse Event. Exacerbation of a pre-existing medical occurrence and symptom including increase in severity of the symptom will be recorded as an AE on the Adverse Event section.

All AEs and serious adverse events (SAEs) are to be reported according to the procedures in Section 9.5.

All clinical laboratory results, vital signs, and ECG results or findings should be appraised by the Investigator to determine their clinical significance. Isolated abnormal laboratory results, vital sign findings, or ECG findings (i.e., not part of a reported diagnosis) should be reported as AEs if they are symptomatic, lead to study drug discontinuation, dose reduction, require corrective treatment, or constitute an AE in the Investigator's clinical judgment.

At each visit, the Investigator or designee will determine whether any AEs have occurred by evaluating the subject. Adverse events may be directly observed, reported spontaneously by the subject or by questioning the subject at each study visit. Subjects should be questioned in a general way, without asking about the occurrence of any specific symptoms. The Investigator must assess all AEs to determine seriousness, severity, and causality in accordance with the

definitions in Section 9.4. The Investigator's assessment must be clearly documented in the site's source documentation with the Investigator's signature.

Always report the diagnosis as the AE or SAE term. When a diagnosis is unavailable, report the primary sign or symptom as the AE or SAE term with additional details included in the narrative until the diagnosis becomes available. If the signs and symptoms are distinct and do not suggest a common diagnosis, report them as individual entries of AE or SAE.

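### Visit 7 stays at Day 98 ±5 for early discontinuers; for a last dose on or before Day 73 its window misses the 14 (±5)-day follow-up period of Section 9.2

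*Combined protocol and SAP*

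**What the plan says.** Table 3.1 in Section 3.3 schedules the three closing visits in different ways.

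- **Visit 5** is Day 84, with footnote a: "Or day of early discontinuation".
- **Visit 6** is last dose + 3 (±1) days. Footnote b sets it at 2 to 4 days after the last dose and names early discontinuation as a case.
- **Visit 7** is Day 98 with a window of ±5 days. Its only marker is footnote c, which concerns the place of the visit. The text around that footnote reads "days after last dose (eg, Visit 5 or early discontinuation). ^c In-home visit unless otherwise specified by Investigator".

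Three sections send early stoppers to Visit 7. Section 5.7.2 requires the early discontinuation/end of treatment "procedures (Visit 5, and Visits 6 and 7: See Table 3.1"). Section 6.4 asks for the procedures of the "end of treatment visit and the follow-up assessments (Visits 6 and 7"). Section 5.1.4 requires emergency-unblinded subjects to stop treatment and adds: "The end of treatment and follow-up assessments for the subjects will be performed as defined in Section 6.4". None of the three gives a different date for Visit 7.

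Section 9.2 collects adverse events up to 14 (±5) "days after the last dose of study medication (ie, the follow-up period"). The AE row of Table 3.1 gives two anchors at once: "All AEs occurring after the subject signs the ICF and up to Day 98 (14 days after last dose) should be collected". The SAE row and the safety time frame in Table 2.1 do the same. The PD time frame in Table 2.1 gives Day 98 without mentioning the last dose.

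**The concern.** The schedule moves the first two closing visits with the last dose and leaves the third on the calendar. A site that reads the Visit 7 column literally would do an early stopper's follow-up check weeks after the two-week point. A site that works from Section 9.2 would do it on time but outside the Table 3.1 window, and Section 15.5 bars deviations except to remove an immediate hazard.

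Four things depend on which reading a site uses:

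- **Off-drug safety check.** Visit 7 carries vital signs, physical assessment, ECG, hematology, coagulation and chemistry. It also carries the last pregnancy test: "Urine pregnancy test to be performed at V2, V3, V4, V5, and V7".
- **Visit 7 ALP and PLP.** Section 11.5.3 summarizes biomarkers by group over time. Visit 7 values could combine about 14 days off drug with 50 to 88 days off drug.
- **AE cut-off.** Section 11.6.1 defines treatment-emergent events with no end date, so the collection cut-off decides which late events count.
- **Contraception.** Inclusion criterion 5 ends the obligation at the follow-up visit.

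Safety and the PD dose response are both primary objectives. Subjects who stop early, some of them because of adverse events, are those for whom a timely check matters most.

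**Working it through.** **Inputs.** Visit 7 is Day 98 ±5 (Table 3.1). Visit 6 is 2 to 4 days after last dose (Table 3.1, footnote b). Follow-up ends 14 (±5) days after last dose (Section 9.2). Let L be the study day of the last dose.

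**Windows.**
- Visit 7 as written: 98 − 5 = 93 to 98 + 5 = 103.
- Section 9.2: L + 14 − 5 = L + 9 to L + 14 + 5 = L + 19.

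**The plan's own figure.** For L = 84, 84 + 14 = 98, and the Section 9.2 window is Days 93 to 103, the same as Visit 7. Day 98 is therefore right for a full course. If the last dose falls anywhere in the Visit 5 window (Days 81 to 87), L + 14 is Day 95 to Day 101, still inside the Visit 7 window.

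**Where the rules part.** They share no day when L + 19 < 93, that is, L ≤ 73. At L = 73 the Section 9.2 period ends on Day 92. At L = 74 the two share Day 93 only.

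**Sensitivity to the reading of Section 9.2.**
- Read as a collection period running from L to L + 19, the cut-off is the same, Day 73.
- Read strictly as L + 14 with no tolerance: L + 14 < 93 gives L ≤ 78.
- Keeping the ±5 but comparing with the nominal Day 98 alone: L + 19 < 98 also gives L ≤ 78.

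**Worked cases.**

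| Last dose L | Section 9.2 window (L+9 to L+19) | Visit 7 opens after that window closes by | Visit 7 days off drug (93−L to 103−L) |
|---|---|---|---|
| 15 | 24 to 34 | 93 − 34 = 59 days | 78 to 88 (nominal 98 − 15 = 83) |
| 43 | 52 to 62 | 93 − 62 = 31 days | 50 to 60 (nominal 98 − 43 = 55) |
| 73 | 82 to 92 | 93 − 92 = 1 day | 20 to 30 (nominal 98 − 73 = 25) |
| 84 | 93 to 103 | windows coincide | 9 to 19 (nominal 14) |

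**AE cut-off.** For a Day 43 stop, the two anchors in the AE row are Day 98 and Day 43 + 14 = 57, which are 41 days apart.

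**After the change.** With Visit 7 at L + 14 (±5), it matches Section 9.2 for every L and stays at Days 93 to 103 for L = 84. Visit 6 closes at L + 4 and Visit 7 opens at L + 9, so the two do not collide.

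**The case against.** The strongest reply is that the intended date can already be read from the document. The Visit 7 column is headed as follow-up, Section 9.2 uses the same ±5 around last dose + 14, the AE and SAE rows equate Day 98 with that point, and the synopsis describes a two-week safety check. On this view only a footnote is missing. The intent is granted. But the equation of the two dates sits in the AE and SAE rows and the safety time frame. It does not move the visit, and for an early stopper it names two different days. Since the table states the early-stop rule for Visits 5 and 6, a site could fairly take its absence at Visit 7 as deliberate.

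Second, Section 9.2 limits AE recording and does not schedule a visit, so treating L + 9 as an opening day is a construction. That is fair, but the Day 73 cut-off does not depend on it.

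Third, safeguards remain:

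- Section 5.7.2 follows a subject withdrawn for an adverse event until it resolves or stabilizes.
- Section 9.2 follows all SAEs to an outcome or loss to follow-up, and related late SAEs stay reportable.
- Section 9.7 covers pregnancies within 30 days of stopping.
- Visits 5 and 6 give checks at the stop and a few days later.
- A late Visit 7 lengthens contraception, which is the cautious direction.

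These points reduce the harm. None of them supplies the scheduled two-week ECG, laboratory tests, pregnancy test, ALP and PLP.

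Fourth, no discontinuation rate is given, the trial is small (four arms of about 12 to 16, so 48 to 64 subjects), and the biomarker analysis is descriptive. This stands: the effect on arm-level results is probably small.

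**Conclusion.** The concern holds. Followed literally, Table 3.1 gives the wrong Visit 7 date for early discontinuers. For any last dose up to Day 73, no Visit 7 date within its window also lies in the Section 9.2 follow-up period. The excess delay grows the earlier the stop: 50 to 60 days off drug for Day 43 and 78 to 88 days for Day 15, against an intended 9 to 19. Subjects whose last dose is on or near Day 84 are essentially unaffected.

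The conclusion rests on the visible text. Figure 3.1 is not shown, part of Section 3.1 is missing, and the superscript on Day 98 is read as footnote c, which agrees with Section 6.3 on in-home visits. The number of subjects affected and the effect on TEAE incidence cannot be derived from the documents. The point should be corrected, but it does not threaten the trial's main comparisons.

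**What to change.** Add a footnote to Visit 7 in Table 3.1, in the style of footnote b: *To be scheduled 14 (±5) days after last dose (Day 98 for subjects whose last dose is on Day 84).* Use the same last-dose anchor in place of Day 98 in the AE and SAE rows, in the safety and PD time frames of Table 2.1, and in the synopsis. The footnote does most of the work; the other edits remove the double anchor and the PD time frame's bare Day 98.

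The cost is one footnote and a few wording changes, with no added visits, samples or analyses and no change for a Day 84 last dose. Under Section 15.7 an amendment goes through the same review and approval as the original protocol, so this is best carried in the next amendment made for other reasons.

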6.3. Treatment Period

Approximate visit durations are expected to be:

- Visits 1, 6, and 7: a few hours
- Visit 3 and 4: more than 6 hours
- Visits 2 and 5: more than 10 hours

Visits 1 through 5 are fasting visits (overnight fast [≥8 hours]). Study participants will be allowed to eat after the first blood collection.

Visits 6 and 7 will be conducted as in-home visits unless requested by the study participant or Investigator.

Study participants should withhold the intake of vitamin B6 or vitamin B6-containing supplements on the day of the study visits (Visits 1 to 7). Vitamin B6 or vitamin B6-containing supplements can be resumed after all study-related procedures are completed.

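### Does Table 3.1 call for a nonfasted ALP, PPi and PLP sample at a screening visit that Section 6.3 makes a fasting visit?

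*Combined protocol and SAP*

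**What the plan says.** In Table 3.1 (Section 3.3), the row for ALP, PPi and PLP marks Visit 1 with the footnote "Single timepoint sample collection". The note to that row reads "All samples will be obtained under nonfasted condition except for the predose samples (Visits 2 to 5"), those predose samples following an overnight fast. It goes on to the withholding of vitamin B6 on visit days and ends "See Section 6.3 for additional details".

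Section 6.3 states "Visits 1 through 5 are fasting visits", with an overnight fast of at least 8 hours, and "Study participants will be allowed to eat after the first blood collection".

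Three other rows of Table 3.1 bear on Visit 1:

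- Hematology: "Fasting required. Blood collection should follow ECG and vital signs if indicated at same time point".
- Chemistry: fasting at every visit "except the postdose visit (Visit 6").
- Urine: "Fasted, use spot urine".

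Section 8.2 gives no fasting rule for the PD samples and refers back to Tables 3.1 and 3.2. Section 8.1 does give one for the PK samples: no fast is needed apart from the predose draws. Section 4.2 applies the exclusions for PLP above the upper limit and ALP below the lower limit at screening. Section 11.5.3 takes as biomarker baseline the latest available value before dosing starts.

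**The concern.** The exception in the PD row names predose samples at Visits 2 to 5 only. No drug is given at Visit 1, so the screening sample falls under the general rule and reads as nonfasted, on a day when everything else is to be collected fasted.

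Two things could be at stake.

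- **Eligibility.** In the visible text the PD row is the only source of a screening PLP. If sites read the row differently, the PLP exclusion could be applied to samples taken under different conditions. The same might hold for ALP, although Section 9.8 does not list the chemistry analytes, so it is unclear which draw supplies it.
- **Baseline.** If a participant's Visit 2 predose value is missing, the screening value becomes baseline. A possibly nonfasted value would then be set against fasted predose values at Visits 3 to 5.

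A related mismatch appears at Visit 7. Hematology and chemistry call for fasting there, Section 6.3 does not list it as a fasting visit, and the PD row makes its sample nonfasted.

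**Working it through.** No figure in the plan is in question, so the check sets the passages side by side.

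| Visit | Section 6.3 | Hematology | Chemistry | Urine | PD, first or only sample |
|---|---|---|---|---|---|
| 1 | fasting | fasting | fasting | fasting | nonfasted as worded |
| 2 | fasting | fasting | fasting | fasting | fasting |
| 3 | fasting | fasting | fasting | not taken | fasting |
| 4 | fasting | fasting | fasting | not taken | fasting |
| 5 | fasting | fasting | fasting | fasting | fasting |
| 6 | not listed | not taken | exempt | not taken | nonfasted |
| 7 | not listed | fasting | fasting | not taken | nonfasted as worded |

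The instructions agree at 5 of 7 visits and differ at 2. At Visit 1, four statements call for fasting and one reads otherwise. The wording covers every screened participant, including the 4 × 12 = 48 to 4 × 16 = 64 to be randomized. That counts people under the wording, not people affected by it.

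**What nonfasted means in this protocol.** The PK row of Table 3.1 states almost the same rule as the PD row: nonfasted, apart from predose samples after an overnight fast. Section 8.1 restates that PK rule as fasting not being required apart from the predose samples. The two describe the same PK samples, so the protocol uses nonfasted to mean that a fast is not required, not that a meal is. The PD row borrows the PK sentence. Its mention of Visits 2 to 5 fits the fact that predose samples exist only at those visits, and need not be a deliberate exclusion of Visit 1. On this reading a fasted Visit 1 sample breaks no instruction.

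**What happens on the day.** Participants arrive at Visit 1 after an overnight fast and may eat once blood has been drawn. Hematology, chemistry and urine are collected fasted, and the PD sample is a single draw. A nonfasted PD sample would need a meal and a second venipuncture. No visible text directs either, and Table 3.2, which sets the within-day order, covers Visits 2 to 5 only.

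**What reaches the analysis.** Baseline is normally the Visit 2 predose value, which is fasted under every passage. The screening value replaces it only when that sample is missing, and Section 11.10 leaves missing-data handling to the SAP. Both samples precede dosing under a double blind, so their fasting state cannot depend on the drug received. Visit 6 PD samples are nonfasted under every passage and are still summarized as change from baseline, so the plan already accepts an unmatched fasting state at some visits.

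**Visit 7.** If nonfasted means fasting not required, the PD row conflicts with nothing there. What is left is Section 6.3 against the hematology and chemistry rows, which touches neither eligibility nor baseline.

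**The case for a change.** The strongest reply is that the PD row is phrased as an instruction, not a permission. Section 8.1 governs PK samples only, Section 8.2 is silent for PD, and the pointer to Section 6.3 follows the vitamin B6 sentence, not the fasting one. A site could draw safety blood fasted, let the participant eat, then take the PD sample, and satisfy both passages to the letter. Two compliant sites could therefore differ on the sample that decides the PLP exclusion. The protocol controls same-day vitamin B6 intake at Visit 1, so leaving fasting unclear sits badly with its own approach. Visit 7 ALP and PLP also fall within the primary PD time frame and are compared with a baseline that is normally fasted.

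Part of this stands. The wording is loose, and the permissive reading is strongly indicated by the PK parallel but not stated for PD. What does not follow is a consequence. The divergent practice needs an extra meal and an extra draw that nobody is told to arrange. The vitamin B6 control, the one intake restriction tied specifically to the PD row, applies at Visit 1 whatever the fasting state. If ALP comes from the chemistry draw, that draw is fasted. At Visit 7 all arms follow the same instructions, so the comparison with placebo is like with like.

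**Conclusion.** This is a clerical slip: a fasting exception written around predose samples that does not mention the screening sample. Sites following Section 6.3 will collect that sample fasted, and the usual baseline is fasted in any case. The documents give no food effect on ALP, PPi or PLP, so the size of any effect is unknown and may be zero. The fallback-baseline route reaches only participants without a Visit 2 predose value, a number the documents do not state.

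Recording fasting status at each PD draw, or flagging screening-value baselines in the summary, would add work with no shown gain. If the protocol is amended for other reasons, the PD row could be aligned with Sections 6.3 and 8.1, and Section 6.3 with the hematology and chemistry rows for Visit 7. Nothing in the analysis depends on it.

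The conclusion rests on two assumptions: that nonfasted carries the same meaning in the PD row as Section 8.1 gives it for PK, and that the text not shown (Table 3.2, redacted rows and most of Section 8.3) contains no instruction for a separate post-meal draw at screening.
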